### **APPROACH:**

This is a prospective, open label study of SCIG for the treatment of patients with CIDP who are dependent on IVIG for control of symptoms.

**Participants:** Up to 30 patients with IVIG-dependent CIDP will be enrolled. To qualify, a patient must meet **ALL** of the inclusion criteria and **NONE** of the exclusion criteria.

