Specific Aim #4. To test the hypothesis that SCIG is efficacious in controlling the symptoms of CIDP.

Clinical response to SCIG will be monitored using HHD and 20-ft timed walk. Data from pretreatment and SCIG treatment phase will be compared. The HHD will measure force generated by the following muscle groups: Shoulder flexion, elbow flexion, elbow extension, wrist extension, first dorsal interosseous (hand), hip flexion, knee extension, knee flexion, ankle dorsiflexion. Measurement will be done bilaterally in duplicates. For the primary efficacy endpoint, HHD muscle strength measured at Week 24 will be compared to HHD muscle strength measured at baseline (pretreatment)

Secondary End-Point.

1. Progression of symptoms requiring reversion to IVIG, initiation of PLEX or other medications, or hospitalization.

**Study Timeline and Feasibility:** Participants will be recruited from the USF Neuromuscular Clinic. This Clinic is the tertiary referral center for the west coast of Florida, with a population of more than 4 million in the Tampa Bay region alone. We estimated that we have more than 70 patients with CIDP. In addition, we see an average of 2 new CIDP patients per month. Thus, there are enough patients for a 3 to 1 screening to enrollment ratio. Planned recruitment is an average of 1 patient every 1.5 months, for a total of 22.5 months. This schedule will place the final recruit completing the trial during month 30 and afford time during the final 6 months of the study for analyzing and preparing data for publication. This planned recruitment timeline is feasible given the size, established referral patterns, and historical recruitment experience of this clinic.

**Rescue protocol:** If a subject worsens (or “relapses”) during the study, we will institute a rescue protocol. Relapse is defined as a 20% decrease in force (as detected on HHD) in more than 50% of the muscles tested when compared to baseline. In case of relapse, we will quantify the serum Ig levels, give IVIG 1 g/kg boost followed by SCIG at 2 g/kg per month. If the subject is already on 2 g/kg per month of SCIG, we will switch the patients back to IV administration and/or institute other treatment options (steroids, PLEX). Please see algorithm in Appendix 2. We will also switch back to IVIG if, at any point during the study:

- a. The subject requests the switch due to treatment failure, adverse events or patient preference.

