- b. The investigators consider it to be in the best interest of the subject (i.e., due to intolerable side-effects, pregnancy, or noncompliance).

**Potential Pitfalls and Alternative Strategies:** There is the potential that some patients may lose interest or become too reticent in performing self-administration. Since compliance may be an issue with self-administration of an injectable medication, serum IgG levels will be done to monitor patient’s adherence to protocol. The use of a home journal for recording therapy and a weekly telephone call will encourage compliance. In the scenario where there is concern with patient compliance, a weekly home therapy visit will be done. Attrition is also expected during the course of the study. If a participant becomes a ‘drop out,’ his or her data will be used in the analysis using an intention to treat protocol. Finally, while recruitment can be an issue in clinical trials, our planned enrollment rate of an average of 1 patient per 1.5 months is feasible. Furthermore, we already identified several patients who are appropriate for this trial. With an average of 2 new CIDP patients seen per month in the USF Neuromuscular Clinic, we should be able to recruit the remaining patients in the proposed timeline. Furthermore, there are many more CIDP patients in the greater Tampa region who are not being seen at USF. Thus, there is an untapped pool of subjects available. In the unanticipated scenario that we fall behind on subject recruitment, we have incorporated 6 additional months in our timeline for analysis and manuscript preparation that could be utilized for subject recruitment and treatment.

**Data Management and Quality Control:** Physiologic and questionnaire data will be collected across two time points (pre- and SCIG treatment phase) by the PI and coordinator who are all proficient in these testing methods. To ensure participant confidentiality, data will be coded to remove patient identifiers into a password-protected database (Excel) on a central computer system that is backed up daily. Data accuracy will be verified by double data entry. All original paper questionnaires will be locked in the PI’s office with only coded identifying information. There will be an interim analysis done after 8 patients have completed the study.

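### Does a recruitment schedule that yields about 15 patients conflict with an enrolment figure of up to 30?

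*Combined protocol and SAP*

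**What the plan says.** The Participants paragraph under Approach gives one enrolment figure: "Up to 30 patients with IVIG-dependent CIDP will be enrolled".

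Study Timeline and Feasibility gives the schedule: "Planned recruitment is an average of 1 patient every 1.5 months, for a total of 22.5 months". It continues: "This schedule will place the final recruit completing the trial during month 30", and leaves a final six months for analysis and publication, so the study lasts 36 months in all. The same section puts the supply at more than 70 existing patients plus an average of 2 new ones a month, and concludes: "Thus, there are enough patients for a 3 to 1 screening to enrollment ratio".

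Potential Pitfalls and Alternative Strategies repeats the rate ("our planned enrollment rate of an average of 1 patient per 1.5 months is feasible"), notes that "we already identified several patients who are appropriate for this trial", and offers a reserve should recruitment fall behind: "we have incorporated 6 additional months in our timeline for analysis and manuscript preparation that could be utilized for subject recruitment and treatment".

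The paragraph on sample size and statistical analysis gives a significance level of 0.05 and a paired Wilcoxon test, chosen partly because the sample is small. It gives no target number, power, effect size or standard deviation. Data Management and Quality Control adds: "There will be an interim analysis done after 8 patients have completed the study".

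**The concern.** A reader looking for the planned sample size has two places to take it from, and they differ by a factor of two. The ceiling suggests 30; the rate multiplied out over the recruitment period gives 15. A slip in one number does not explain the gap, because the rate appears twice in the same form. Nor does the reserve close it.

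The number matters for interpretation. The primary endpoints are withdrawals for side effects and for laboratory abnormalities, so the number of patients determines how low a withdrawal rate the study can support. It also determines how large a change in strength or quality of life the paired comparisons can detect. If the sponsor really intended 30, the timeline would be badly short. If the sponsor intended 15, a reader who assumes 30 expects more from the study than it can give.

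**Working it through.** **Inputs.** One patient per 1.5 months; 22.5 months of recruitment; last completion during month 30; final six months, usable as a reserve; more than 70 existing and 2 new patients a month; 3 screened per enrolled (all from Study Timeline and Feasibility or Potential Pitfalls). Treatment lasts 24 weeks (Specific Aim #2), which is 168 / 30.44 = 5.5 months. The ceiling is 30 (Participants). The interim comes at 8 completers (Data Management).

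**1. Does the schedule agree with itself?**
- Patients enrolled: 22.5 / 1.5 = 15, or 16 if the first enters at month 0.
- Last patient completes: 22.5 + 5.5 = month 28.0. This precedes month 30 and leaves about two months for the follow-up visit and slippage.
- Total: 30 + 6 = 36 months.

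The stated figures fit together for a study of about 15.

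**2. What does the reserve add?**
- Recruitment extended by six months: (22.5 + 6) / 1.5 = 19, or 20 with a first entry at month 0.
- Counting back from month 36 with 24 weeks of treatment: (36 − 5.5) / 1.5 = 20.3, so 20, or 21 with a first entry at month 0.
- Counting back with the plan's own allowance of 30 − 22.5 = 7.5 months after the last entry: (36 − 7.5) / 1.5 = 19.

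The range is 19 to 21.

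**3. What would 30 need?**
- At the stated rate: 30 × 1.5 = 45 months of recruitment. Last completion falls at 45 + 5.5 = month 50.5, or 45 + 7.5 = month 52.5 on the plan's own allowance.
- In 22.5 months: 22.5 / 30 = one patient every 0.75 months, twice the stated rate.
- Reading the rate the other way, 1.5 patients a month, gives 1.5 × 22.5 = 33.75. That is not 30, and the repeated statement of the rate rules it out.

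**4. Is the patient supply the limit?** No. Existing plus new patients come to 70 + 2 × 22.5 = 115, and 115 / 3 = 38 enrolments at 3 to 1. The supply statement holds for 15 and also for 30. Only the average rate separates the two.

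**5. What depends on the number?** For zero withdrawals among n patients, the exact two-sided 95% upper limit is 1 − 0.025^(1/n). For the paired Wilcoxon test, the detectable standardized change is calculated from the noncentral t with 0.955 n effective pairs. The 80% power, two-sided 0.05 and efficiency of 0.955 are assumptions made here; the plan gives only the 0.05.

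| n | upper limit, no withdrawals | detectable change | interim, 8 / n |
|---|---|---|---|
| 15 | 21.8% | 0.80 | 53% |
| 20 | 16.8% | 0.68 | 40% |
| 30 | 11.6% | 0.54 | 27% |

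The differences are real, but none contradicts a figure in the plan, because the plan gives no limit, effect size or power. The interim is triggered by a count of completers and needs no total.

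**The case for a change.** The strongest case for a change is that a maximum is no substitute for a planned number. The section headed sample size contains none, and the plan's own schedule cannot reach the maximum even with the whole reserve spent. The patients already identified do not rescue it: the rate is described as the average for planned recruitment as a whole, so they are already counted in it. The cost of stating a number is a sentence or two, and the primary endpoints are of the kind whose precision depends almost entirely on n.

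Most of this stands as description. The schedule does imply about half the ceiling, and a stated target with its precision would help a reader. Two parts do not stand. First, a planning average is not a cap: the plan also points to patients in the region not yet seen at the clinic, which is a reason to set the ceiling above the scheduled number. Second, asking for the schedule to be rebuilt around 30, by doubling the rate or by recruiting for 45 months, treats a permitted maximum as a goal the plan never set.

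The text reviewed also lacks the opening pages, so the absence of a target can be asserted only for what was available.

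**Conclusion.** No change to the plan follows. The arithmetic is right: the schedule gives 15 to 16 patients, or 19 to 21 with the full reserve, against a ceiling of 30. It exposes no wrong figure, because 15 lies within the ceiling and the rate, duration, completion month and reserve are mutually consistent.

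If the plan is followed exactly, the analyses are the same at any number enrolled. The paired Wilcoxon test and the withdrawal counts use the patients actually treated, and an analyst would report the interval at that number. The upper limit of 21.8% rather than 11.6%, and the detectable change of 0.80 rather than 0.54, describe how modest a study of 15 is. The plan, which calls itself a pilot and its sample small, does not claim otherwise. The upper limits assume no withdrawals, and the detectable changes rest on the assumptions given with the table. The conclusion does not depend on either: what is missing is a reported planning number, and its absence biases nothing.

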**Exclusion Criteria:**

- 1) Thrombocytopenia or other bleeding disorders;
- 2) Patients on anticoagulation therapy with an INR > 3.5;
- 3) Severe or anaphylactoid reactions to IVIG;
- 4) Cancer (active or currently treated);
- 5) Pregnancy;
- 6) Breast-feeding;
- 7) Renal insufficiency (creatinine > 1.5 upper limit of normal) or failure;
- 8) Congestive heart failure;
- 9) Psychiatric illness that would interfere with ability to provide informed consent or adhere to protocol;
- 10) Current IVIG doses greater than 2 g/kg per month;
- 11) Subject with an IgA level < 5% lower limit of normal;
- 12) History of active infection with HIV, Hepatitis B or Hepatitis C;
- 13) Presence of any other medical condition, which in the opinion of the investigator might interfere with performance;
- 14) Participation in a trial of an investigational medicinal product for CIDP in the past 12 weeks.

**Sample size and statistical analysis:** Descriptive information for the rate of change, such as mean and standard deviation, will be calculated. Due to the small sample size and self-control used in this study, instead of using paired t-test, Wilcoxon paired ranked test will be used to compare the change of before and after from each patient. Significance level is defined as 0.05 and all of the analyses will be carried by SAS (version 9.2).

**DESIGN:** The study will be submitted to the USF IRB for approval.

**Specific Aim #1.** We will assess QOL using the Medical Outcome Study 36-item short form health status scale (SF-36) and the Rasch-built Overall Disability Scale (R-ODS). The scales have been validated in patients with CIDP (Merkies et al, 2002; van Nes et al, 2011). We will also do a survey of side effects and satisfaction with treatment (using the Treatment Satisfaction Questionnaire for Medication, or TSQM) and CIP-PRO20 scale (used by permission from [name]; see appendix 3). No surveys will be completed until the patient signs the ICF. In addition, we will determine whether patients currently treated with IVIG would be willing to try the SC route of administration. Reasons cited for unwillingness to switch will be collected.

Specific Aim #2. To test the safety and tolerability of SCIG and feasibility of self-administration in patients with CIDP.

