1. CBC with differential count and platelet count will be done prior to treatment and once per month during treatment.
2. Symptom monitoring will be done via phone and at scheduled visits at regular intervals. Study visits will have a window of +/- 7 days. Patients will have 24/7 access to investigators to report any symptoms that develop.
3. Subjects will be provided with emergency contact number for questions relating to any symptoms during the study.
4. In the event that the subject experiences a reaction at home, they will call us. They will also be trained to call 911 in an emergency situation.

Primary End-Points.

1. Significant side-effects requiring withdrawal from study.
2. Laboratory abnormalities requiring discontinuation of study.

**Table 2.** Schedule of Study Events and Visits.

	Screening	Day 1	Week 1	Week 2*	Week 3*	Week 4 (Month 1)	Week 8 (Month 2)	Week 12 (Month 3)	Week 16 (Month 4)	Week 20 (Month 5)	Week 24 EOS/ET (Month 6)	Follow-Up
	V1	V2	V3	V4	V5	V6	V7	V8	V9	V10	V11	V12
Informed Consent	x											
Inclusion/Exclusion Review	x	x										
Medical History	x	x	x									
Vital Signs Monitoring	x	x	x	x	x	x	x	x	x	x	x	
Physical/Neuro Exam	x	x	x			x	x	x	x	x	x	x
TSQM	x	x	x			x	x	x	x	x	x	
CIP-PRO20	x	x	x			x	x	x	x	x	x	
R-ODS	x	x	x			x	x	x	x	x	x	
SF-36	x	x	x			x	x	x	x	x	x	
Hand-held Dynamometry	x	x	x			x	x	x	x	x	x	
20-ft Timed Walk	x	x	x			x	x	x	x	x	x	
Electrocardiogram (ECG)	x											
PT/INR, PTT	x											
TSH	x											
Quantitative IgA, IgG, IgM	x	x				x	x	x	x	x	x	
Hematology, blood chemistry	x		x			x	x	x	x	x	x	x
Urine Pregnancy Test	x	x	x			x	x	x	x	x	x	
Subcutaneous Drug Administration Training	x	x	x	x								
Subcutaneous Drug Administration	x	x	x	x								
Drug Diary Training	x	x										
Drug Diary Review				x	x	x	x	x	x	x	x	
Drug Dispensation	x	x	x	x	x	x	x	x	x	x	x	
Drug Accountability							x	x	x	x	x	

\* optional for additional administration training (can be completed at home)

Specific Aim #3. To test the hypothesis SCIG is associated with better QOL.

At baseline (pretreatment of SCIG, while subjects are being treated with IVIG), QOL and treatment satisfaction questionnaires (SF-36, CIP-PRO20, R-ODS, and TSQM) will be done. These measures will be repeated monthly during the course of the study. Data from pretreatment and treatment with SCIG phase will be compared using appropriate statistical methods with correction for multiple comparisons.

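### The plan promises intention to treat for drop-outs, but its paired Week 24 strength test excludes anyone without a Week 24 value, and no rule covers early-termination readings

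*Combined protocol and SAP*

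**What the plan says.** Four places in the protocol bear on this.

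- **Potential Pitfalls and Alternative Strategies:** "Attrition is also expected during the course of the study", and for a drop-out "his or her data will be used in the analysis using an intention to treat protocol". No drop-out rate, analysis set or missing-data method is given.
- **Specific Aim #4 (design section):** for primary efficacy, "HHD muscle strength measured at Week 24 will be compared to HHD muscle strength measured at baseline (pretreatment").
- **Sample size and statistical analysis:** "Wilcoxon paired ranked test will be used to compare the change of before and after from each patient". The level is 0.05 with no side stated. No other test is named.
- **Table 2:** the last treatment-phase column, V11, is headed "Week 24 EOS/ET (Month 6"). It serves both the Week 24 visit and an early-termination visit, and HHD is marked in it. The monitoring list above the table adds: "Study visits will have a window of +/- 7 days".

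Continued observation after stopping SCIG is stated only for a patient who becomes pregnant (Specific Aim #2). For other patients who stop, the protocol does not say whether they are followed to Week 24.

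**The concern.** A signed-rank test works on within-patient differences. A patient with a baseline reading and no Week 24 reading has no difference and drops out of the test. Followed literally, the named test therefore gives a completers-only analysis, which is the opposite of what the intention-to-treat sentence promises.

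The shared V11 column offers a second route. A patient who leaves at, say, Week 8 has an HHD reading in the column headed Week 24. Nothing states whether it may be used as the Week 24 value, although it lies far outside the visit window. Someone could settle that after seeing the data.

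The direction matters because this is a single-arm, open-label study in IVIG-dependent patients, where a good result on strength means no decline. Leaving can be related to outcome: the rescue section allows a return to IVIG for treatment failure, adverse events or the investigator's judgement. If those who worsen are the ones missing at Week 24, the remaining pairs look better than the enrolled group. The point concerns patients with no true Week 24 reading, not those who are rescued and stay in follow-up.

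**Working it through.** The protocol gives no power, effect size, SD or attrition rate, so there is no figure of its own to reproduce. The inputs below marked as assumed are for illustration.

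**Inputs**
- Number of patients: "Up to 30 patients with IVIG-dependent CIDP will be enrolled". The recruitment plan implies fewer: 22.5 months / 1.5 months per patient = 15. Both are used.
- Test: Wilcoxon signed-rank at 0.05, two-sided (assumed), counting significant results in the direction of decline.
- Assumed: drop-out d of 10% to 30%; change in HHD with SD 10 percentage points; stayers' mean 0; leavers' true Week 24 mean -20; leavers' ET reading -5 (before most of the decline).

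**Step 1. Pairs left.** N minus the number of drop-outs at d = 10/20/30% leaves 27/24/21 of 30, or 13/12/11 of 15.

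**Step 2. Mean change.** Let S be the stayers' mean, L the leavers' true Week 24 mean and E the leavers' ET mean.
- True mean = (1 - d)S + dL
- Completers-only mean = S, so its bias is S - [(1 - d)S + dL] = d(S - L)
- Mean with ET used as Week 24 = (1 - d)S + dE, so its bias is d(E - L)

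At d = 20%: true = 0.8 x 0 + 0.2 x (-20) = -4.0; completers = 0.0; ET as Week 24 = 0.2 x (-5) = -1.0. At d = 30%: -6.0, 0.0 and -1.5.

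The second bias is zero when E = L, that is, when the ET reading already shows the full decline.

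**Step 3. Chance of a significant decline (simulation).**

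| n, drop-out | Week 24 known for all | Completers only | ET (-5) used as Week 24 | Worst rank for all leavers |
|---|---|---|---|---|
| 15, 20% | 12% | 2% | 4% | 15% |
| 30, 20% | 28% | 2% | 7% | 37% |
| 30, 30% | 58% | 2% | 11% | 77% |

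Repeat runs differ by a point or two.

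**Step 4. Sensitivity to the assumptions (n = 30, 20% drop-out).**
- Leavers truly at -25, early ET still at baseline: decline detected in 32% with the loss counted, 2.5% for completers, 2.6% with early ET as Week 24.
- ET reading taken at full decline (-20): 27% with ET as Week 24, against 27% with full data. No bias.
- Half the leavers unchanged: 9% with full data, 2% for completers, 4% with ET (-5) as Week 24.
- All leavers truly unchanged, but all given the worst rank: a false decline in about 37% of trials (77% at 30% drop-out), against the correct 2% to 3%.

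**Step 5. Does a longitudinal model help?** In one simulation of monthly readings with n = 30, on assumed trajectories, the true change was -6.1, completers gave +1.1 and a likelihood-based repeated-measures estimate gave -3.7. The model removed 1.1 - (-3.7) = 4.8 of the 1.1 - (-6.1) = 7.2 points of bias, about two-thirds. This shows direction, not a forecast.

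**The case against.** **Table 2 is a schedule of procedures, not an analysis rule.** This stands. A reader might infer that the plan will analyse drop-outs as stable at Week 24, but no sentence says so. The efficacy sentence asks for strength measured at Week 24, and with the 7-day window an early ET reading does not qualify. That leaves the completers-only reading as the literal one, so the conflict with intention to treat remains.

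**An ET reading need not hide failure.** This stands too. A reader might infer that omitting drop-outs and using their ET reading both favour SCIG. The second does so only if the reading precedes the decline. Relapse is defined by a 20% force loss in more than half of the muscles, so a reading taken at relapse records the loss. SCIG starts within 2 weeks of the last IVIG course, so a very early ET reading may still reflect IVIG, but the documents give no timing of departures and do not make it near baseline in general.

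**The failures are counted elsewhere.** Correct: withdrawal for side effects or laboratory abnormalities is the primary end-point, and progression is the secondary end-point. That limits the harm to the strength comparison but does not repair it.

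**Attrition may be unrelated to strength.** The pitfalls section mentions loss of interest and reluctance to self-administer. If that dominates, the bias shrinks, as Step 4 shows.

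**Quality of life.** A reader might extend the point to Aim 3 because V11 also carries the questionnaires. The documents do not support that: they are repeated monthly, pretreatment is compared with the SCIG phase, and no Week 24 end-point is named.

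**Conclusion.** The concern holds in limited form. The stated test defeats the stated principle: a paired test at Week 24 cannot include patients who lack that value, and no rule covers ET readings. If patients leave because they worsen, the completers-only estimate is too favourable by d(S - L), or 4.0 percentage points with 20% drop-out and a 20-point gap between stayers and leavers. Detection at n = 30 then falls from 28% to 2%. Using ET as Week 24 is biased the same way only when the reading comes before the decline.

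The size rests wholly on assumed attrition, timing of departure and SD, and it is small if departures are mostly unrelated to strength. Because the study is a pilot and the losses appear in its primary and secondary end-points, this is a change that should be made rather than a defect that invalidates the trial.

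**What to change.** 1. **Separate the visits.** Record ET apart from Week 24 with its actual study week, and state that an ET reading is not labelled Week 24.
2. **Name one main estimate.** Estimate the Week 24 change in HHD from a repeated-measures model using every enrolled patient's monthly and ET readings at their actual time. Use a simple covariance structure, because n is 15 to 30.
3. **Name the sensitivity analyses.** Report the completers-only paired Wilcoxon. Add a signed-rank analysis giving the worst rank only to patients who left because of worsening, not to those who left for side effects alone, who may have lost no strength. State that it is deliberately conservative: it exceeded full-data detection in Step 3 (37% against 28%).

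The cost is one schedule column and a few sentences of analysis text. HHD is already scheduled monthly, so no visits or patients are added. The downsides are a model assumption in a small sample, a bias that is reduced rather than removed, and a less favourable strength estimate if patients leave early.
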